| Diagnosis and Main Inclusion Criteria | 
Main Inclusion Criteria:
 
 • Histopathologically confirmed diagnosis of metastatic advanced cutaneous squamous cell carcinoma. • History of solid-organ transplant requiring immunosuppression • Age ≥ 18 yrs • Measurable disease by RECIST v1.1 • KPS $\geq 60\%$, ECOG ≤ 2 • No prior JAK Inhibitor therapy • Adequate organ function • All clinically significant toxicities from prior systemic therapy must be \leq Grade 1 (with the exception of alopecia, and peripheral neuropathy, which may be \leq grade 2). • Subjects must agree to undergo tumor biopsies until biopsies have been obtained from 10 subjects (i.e., biopsies are required in at least the first 10 enrolled subjects, or until a goal of 10 study biopsies are obtained). Subjects in whom a biopsy is technically not feasible or in whom would result in unacceptable risk in the opinion of the investigator, may be exempted from the biopsy requirement with discussion with the principal investigator. • Negative pregnancy test for women of child bearing potential • Ability to take oral medications • Adequate marrow function: 
 - ANC ≥ 1000 /mm³ - Platelet count $\geq 50,000$/mm³ - Hemoglobin ≥ 8.0g/dL (not requiring transfusion in the past 2 weeks) |
| Study Product, Dose, Route, Regimen | Ruxolitinib will be administered orally twice daily during the entirety of each 28-day cycle. There will be a safety lead-in cohort of 6 patients who receive the starting dose of 15mg twice daily (BID). If dose limiting toxicities (DLT) are seen in 1 or fewer patients, the starting dose for all remaining patients will be 15mg BID. If DLT's are seen in >1 patient, another 6 patients will be enrolled at 10mg BID. If DLT's are seen in 1 or fewer patients, the starting dose for the remaining patients will be 10mg BID. Otherwise the study will be terminated. Individual subjects may have dose reductions of ruxolitinib during the course of treatment, based upon safety laboratory assessments. |

| | |
|-----------------------------------|---|
| Duration of administration | Treatment with ruxolitinib will commence following enrollment and continue until objective disease progression as confirmed by RECIST v1.1, intolerable toxicity or the occurrence of another discontinuation criterion. |

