5. STUDY DESIGN

5.1 General Design

This is an open-label, multi-center, Phase II study to evaluate the efficacy of ruxolitinib in post-transplant patients with advanced cutaneous squamous cell carcinoma.

Study Intervention: In a safety lead-in of 6 patients, subjects will receive ruxolitinib 15mg BID. After 4 weeks, if dose-limiting toxicities (DLT) are observed in 1 or fewer patients, the study will enter stage 1 of the Simon two-stage design where all subsequent patients will receive a starting dose of ruxolitinib 15mg BID. If more than 1 DLTs are observed, another cohort of 6 patients will be treated at a dose of 10mg BID. If less than 2 DLTs are observed at the new dose of 10mg, then the study will proceed to stage I using this dose; otherwise the study will stop.

Individual subjects may have dose reductions of ruxolitinib during the course of treatment, based upon safety laboratory assessments.

Schedule of Evaluations: Subjects will have regularly scheduled study visits at the clinical site on Day 1 and Day 15 (\pm 3 days) of the first cycle, then on Day 1 (\pm 3 days) of every subsequent cycle (starting cycle 2), where safety assessments, including laboratory assessments, vital signs, and physical examinations will be performed (see Section 12 for study calendar).

Response to treatment will be determined by CT scans of the chest, abdomen, and pelvis with contrast. The overall response rate for the primary endpoint evaluation will be determined by RECIST v1.1 criteria. In patients who are unable to get a CT scan w/ contrast due to renal function (or any other reason), an MRI with and without contrast may be used instead. Imaging will be performed at the following time points:

| | |
|--------------------------------------|---|
| Baseline scan | Baseline scan within 4 weeks prior to first treatment |
| Weeks 1 – 32 | Every 8 weeks +/- 1 week (at weeks 8, 16, 24, 32) |
| Weeks 33 – until disease progression | Every 12 weeks +/- 1 week (at weeks 44, 56, 68, 80, 92, 104) |
| 2 years | If subjects achieve ongoing disease control at 2 years, patients will be continued on study treatment and observed with imaging every 12 weeks +/- 2 weeks. |

Duration of treatment: Subjects will continue treatment until confirmed radiographic disease progression, intolerable toxicity or side effects (Section 6.5.1).

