5.2 Number of Patients

Utilizing a Simon Two-Stage Mini-Max design, 18 patients with advanced cSCC will be accrued in the first stage. If 1 or more patients achieve a response, then an additional 14 will be accrued. If 3 or fewer responses are seen, the study will be declared negative. If the initial safety lead-in does not result in advancement to stage I, an additional 6 patients will need to be accrued for a second safety lead-in. Assuming a 10% drop-out rate, we anticipate a total accrual of 35 patients with a maximum potential accrual of 41 patients (see Statistical Considerations).

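### Section 5.1 states the safety lead-in rule partly in patients and partly in DLTs, so one toxicity outcome receives two answers (minor)

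*Combined protocol and SAP*

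**What the plan says.** Section 5.1 (General Design) treats six lead-in patients at 15 mg BID and then gives three instructions.

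- Stay at 15 mg: "After 4 weeks, if dose-limiting toxicities (DLT) are observed in 1 or fewer patients". The unit is patients.
- De-escalate: "If more than 1 DLTs are observed, another cohort of 6 patients will be treated at a dose of 10mg BID". The unit is DLTs.
- At 10 mg: "If less than 2 DLTs are observed at the new dose of 10mg, then the study will proceed to stage I using this dose". For any other result at that dose, the instruction is: "otherwise the study will stop". The unit is DLTs.

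The Protocol Synopsis (row on study product, dose, route and regimen) states the same rule in patients throughout. It stays at 15 mg if at most one patient has a DLT, and continues: "If DLT's are seen in >1 patient, another 6 patients will be enrolled at 10mg BID". At 10 mg: "If DLT's are seen in 1 or fewer patients, the starting dose for the remaining patients will be 10mg BID". For any other result at that dose, the synopsis says: "Otherwise the study will be terminated".

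Section 5.2 mentions the second cohort without restating the threshold: "If the initial safety lead-in does not result in advancement to stage I, an additional 6 patients will need to be accrued". Section 17.1 does likewise, giving 35 patients, or at most 41 if a second lead-in is needed. Section 15.10 (Stopping Rules) is marked not applicable. No section in the available text defines a DLT or says that a patient counts once.

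**The concern.** A patient can have more than one DLT, so a count of DLTs can exceed a count of patients. A rule whose branches use different units may then leave an outcome with two answers. This rule sets the starting dose for later patients, decides whether six more are enrolled at a lower dose, and can end the trial. If the disputed outcome occurred, the unit would have to be chosen after the toxicity had been seen, by a team spread over three sites.

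**Working it through.** **Step 1: where the texts differ.** Let k be the number of the six patients with at least one DLT, and d the total number of DLTs, so d ≥ k.

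| Outcome | Synopsis | Section 5.1, 15 mg | Section 5.1, 10 mg |
|---|---|---|---|
| k = 0, d = 0 | stay / proceed | stay | proceed |
| k = 1, d = 1 | stay / proceed | stay | proceed |
| k = 1, d ≥ 2 | stay / proceed | stay **and** de-escalate | **stop** |
| k ≥ 2 (so d ≥ 2) | de-escalate / stop | de-escalate | stop |

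Only the third row conflicts. At 15 mg Section 5.1 contradicts itself. At 10 mg it contradicts the synopsis.

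**Step 2: how likely that row is.** The plan states no operating characteristic for the lead-in, so there is no figure to reproduce. Two assumptions are needed, and the documents give neither:

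- p, the per-patient DLT risk: 0.10 to 0.20;
- q, the chance that a patient with a DLT has at least two: 0.10 to 0.50.

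P(exactly one of six patients has a DLT) = 6p(1−p)^5:

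- p = 0.10: 6 × 0.10 × 0.90^5 = 0.3543
- p = 0.20: 6 × 0.20 × 0.80^5 = 0.3932

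Conflict in a given cohort = that value × q:

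- p = 0.10: 0.0354 (q = 0.10) to 0.1771 (q = 0.50)
- p = 0.20: 0.0393 to 0.1966

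**Step 3: a conflicting stop at 10 mg.** The 10 mg cohort exists only if 15 mg fails. Counting patients at 15 mg, P(15 mg fails) = 1 − (1−p)^6 − 6p(1−p)^5:

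- p = 0.10: 1 − 0.5314 − 0.3543 = 0.1143
- p = 0.20: 1 − 0.2621 − 0.3932 = 0.3446 (from unrounded terms)

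Multiplying by the conflict probability at 10 mg:

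| p at 15 mg | p at 10 mg | q = 0.10 | q = 0.50 |
|---|---|---|---|
| 0.10 | 0.10 | 0.0040 | 0.0202 |
| 0.20 | 0.20 | 0.0136 | 0.0678 |
| 0.20 | 0.10 | 0.0122 | 0.0611 |

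A simulation of 2,000,000 trials agreed for the first two rows: 0.0040 and 0.0203, then 0.0135 and 0.0678.

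**Step 4: what the documents suggest about p and q.** Section 10.1 reports, for myelofibrosis, a median onset of about 8 weeks for Grade 3 or 4 thrombocytopenia, 12 weeks for Grade 3 or 4 neutropenia and 1.5 months for first Grade 2 or higher anemia. The lead-in decision comes after 4 weeks. Section 9.2 withholds drug for Grade 3 or 4 toxicity, which limits later second events. Both facts point to the low end for hematologic events. They do not establish it: these are medians from another population, and several cytopenias could appear on one blood count.

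**The case against.** The strongest reply is that this is loose wording, not two designs. The Section 5.1 rule is one chain that opens in patients, its second sentence is plainly meant as the complement of the first, and counting patients is the only reading under which the 15 mg branches do not overlap. The synopsis says the same in every branch. This stands, and it is why the point is minor. It does not remove the point: the literal 10 mg branch in the body of the protocol ends the trial, and no other section settles the unit. Section 10.3 groups related signs and symptoms under one diagnosis, but two distinct toxicities in one patient would still be two events.

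A second reply is that the probabilities rest on assumptions, and that nothing in the documents supports q as high as 0.50. That also stands. A reader might take the per-cohort figures of 3.5% to 19.7% as chances of a wrong decision. They are not. At 15 mg the synopsis and the first clause of Section 5.1 both say stay, and only one clause says otherwise.

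A third reply is that the missing DLT definition matters more, because counting patients does not say which patients count. That is fair, but it is a separate gap. Harmonizing the unit neither depends on it nor cures it.

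**Conclusion.** The rule is wrong as written, because one outcome receives conflicting instructions. The severity is minor. The direct contradiction between Section 5.1 and the synopsis, a stop against a continuation at 10 mg, has an unconditional probability of about 0.4% to 6.8%. This assumes p of 0.10 to 0.20, q of 0.10 to 0.50, and patients counted at 15 mg. The top of the range needs p = 0.20 at both doses together with q = 0.50.

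A reader might infer that the ambiguity could expose later patients to too high a dose. The documents do not support that. In the disputed outcome, literal Section 5.1 lowers the dose or stops, whereas the synopsis stays or proceeds. Individual patients also remain covered by the dose-modification tables in Section 9.2 and the safety monitoring in Section 16.3. Nor is the increase from 35 to as many as 41 patients peculiar to this conflict: it follows from any second lead-in. What can be attributed to the mixed units is an unneeded reduction to 10 mg with its extra cohort of six, or an unneeded stop.

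**What to change.** In Section 5.1 make two replacements, with no other change to the rule:

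- in the sentence that triggers the 10 mg cohort, write the condition as *DLTs are observed in more than 1 patient*;
- in the sentence that governs 10 mg, write it as *DLTs are observed in fewer than 2 patients*.

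Every outcome then falls in exactly one branch, and Section 5.1 agrees with the synopsis.

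Do not add time-window wording such as a limit to the first 4 weeks. In Section 5.1 the 4 weeks says when the decision is taken. The Section 13.1 calendar places C2D1 nominally on day 29, with a window of 3 days either side, and it is the only scheduled blood count after C1D15. A strict 4-week limit could exclude a toxicity first found at that visit.

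The documents do not say whether the lead-in is complete. If it is, a note to file recording which unit was applied should accompany the change. The cost is two phrases in an amendment and possibly that note. No patients, visits or procedures are added, and the Simon design figures are unaffected.

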5.2 Number of Patients

Utilizing a Simon Two-Stage Mini-Max design, 18 patients with advanced cSCC will be accrued in the first stage. If 1 or more patients achieve a response, then an additional 14 will be accrued. If 3 or fewer responses are seen, the study will be declared negative. If the initial safety lead-in does not result in advancement to stage I, an additional 6 patients will need to be accrued for a second safety lead-in. Assuming a 10% drop-out rate, we anticipate a total accrual of 35 patients with a maximum potential accrual of 41 patients (see Statistical Considerations).

5.3 Correlative Studies

5.3.1 Tumor biopsies for pharmacodynamic assessment

The biological activity of ruxolitinib will be assessed by performing paired tumor biopsies

at baseline, and between Cycle 2 Day 1 and Cycle 2, Day 8 of study therapy. These biopsies will be mandatory in the first 10 patients enrolled on Stage I of the study (first 18 enrolled subjects), and optional in subsequent patients. A biopsy at the time of disease progression is optional in all patients. (Note: If sufficient flash frozen tumor material is available from a prior tumor biopsy performed within 3 months of registration with no intervening therapy, then a repeat baseline biopsy will not be necessary.)

A goal of at least 3 cores and up to 8 cores from the patient's tumor biopsy specimen, if safe to obtain, will be obtained for research purposes. The first core will be placed in buffered formalin and paraffin-embedded as standard of care. Subsequent cores will be flash frozen.

5.3.2 Blood Collection

Whole blood will be requested as outlined in section 13.2 for peripheral blood mononuclear cell (PBMC) and circulating tumor DNA (ctDNA) collection to evaluate the effect of ruxolitinib on circulating immune cell populations before and during treatment and to further evaluate ctDNA as a potential biomarker of disease response.

Detailed specimen processing and shipping information can be found in the laboratory manual.

Correlative analysis may include some or all of the following studies:

- IHC and/or Western blot and qRT-PCR to evaluate changes in STAT3, Cyclin D1, and other proteins
- Multiplex immunohistochemistry to assess changes in the immune microenvironment
- Bulk and single cell RNA-Seq analysis may be performed on paired tumor biopsies to assess mechanisms of disease response and resistance
- Additional studies may be performed in the future.

Samples will be stored on-site and shipments will be sent to the [name] laboratory by batch shipments when requested to the address listed below:

[name] Laboratory
Columbia University Medical Center
[name]
[name]
[name]

The analyzing laboratories will be notified by email ([contact]) the day the samples are sent. The email will contain the following information:

- Subject ID

- Subject Initials
- Date of collection
- Time point (e.g. baseline, cycle 2 day 1, end of treatment, etc)
- Name of study center
- Shipment date
- Contents of shipment

Samples should be shipped via courier so that the package is tracked appropriately (specifically Federal Express or UPS). The samples should be shipped for morning delivery, Monday through Thursday for optimal processing.

Samples will be tracked through a Microsoft Excel tracker.

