2.2 Secondary Objectives

- To evaluate the clinical benefit of ruxolitinib as determined by upon progression free survival and overall survival.
- To determine the safety and tolerability of ruxolitinib in post-transplant patients with advanced cutaneous squamous cell carcinoma
- To assess the pharmacodynamics of ruxolitinib in post-transplant patients with advanced cutaneous squamous cell carcinoma.

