14.1.2 Blood samples

Whole blood will be requested as outlined in section 13.2 for peripheral blood mononuclear cell (PBMC) and circulating tumor DNA (ctDNA) collection to evaluate the effect of ruxolitinib on circulating immune cell populations before and during treatment and to further evaluate ctDNA as a potential biomarker of disease response.

See laboratory manual for detailed processing and shipping instructions for all correlative study specimens.

Shipping Instructions:

Shipments will be sent to the [name] laboratory by batch shipments when possible.

[name] Laboratory
[name]
[name]
[name]

The analyzing laboratories should be notified by email (Study listserv email: [contact]) the day the samples are sent. The email will contain the following information:

- Subject ID number
- Subject Initials
- Date of collection
- Time point (e.g. baseline, Cycle 2 Day 1, end of treatment, etc)
- Name of study center
- Shipment date
- Contents of shipment

All samples should be directed to the address listed above. Samples should be shipped via courier so that the package is tracked appropriately (specifically Federal Express or UPS). The samples should be shipped for morning delivery, Monday through Thursday for optimal processing.

Samples will be tracked through a Microsoft Excel tracker.

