21.9 Efficacy analysis/ correlative analysis

Efficacy analysis:

Imaging will be reviewed by a site radiologist and interpreted according to response criteria detailed in section 12.4 for primary and secondary endpoint analysis. Imaging studies may be requested from participating centers for central radiology review.

Correlative analysis:

All tissue and blood samples collected at each site will be sent to Columbia University Medical Center for storage and correlative studies described above.

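### The shipment email tells the analyzing laboratory which specimen is baseline and which is on treatment, and the protocol requires no masked or same-run scoring of the pharmacodynamic pairs

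*Combined protocol and SAP*

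**What the plan says.** Section 5.3.2 states that "The analyzing laboratories will be notified by email" on the day of shipment. The listed contents include subject ID, "Subject Initials", date of collection and "Time point (e.g. baseline, cycle 2 day 1, end of treatment, etc"). Section 14.1.2 repeats the rule ("The analyzing laboratories should be notified by email") with the same items, including "Time point (e.g. baseline, Cycle 2 Day 1, end of treatment, etc").

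Both sections have headings about blood, but the rule is not confined to blood. The assay list in 5.3.2 includes work on tumor tissue, and Section 21.9 says "All tissue and blood samples collected at each site will be sent to Columbia University Medical Center for storage and correlative studies described above".

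Section 2.2 lists as a secondary objective "To assess the pharmacodynamics of ruxolitinib in post-transplant patients with advanced cutaneous squamous cell carcinoma". Sections 3.4 and 5.3.1 make the paired tumor biopsies the data for it: one at baseline and one between Cycle 2 Day 1 and Day 8, in at least 10 subjects (Section 5.1). Section 17.2 plans descriptive summaries and individual profile plots for pharmacodynamic parameters. For the correlative markers it plans Fisher's exact or Wilcoxon rank sum tests against response status, labelled exploratory.

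**The concern.** The pharmacodynamic readout is a within-patient change with no untreated comparison. If the person scoring a stained section or a blot knows which specimen came after treatment, any tendency to score it lower goes straight into the estimated change. No feature of the design would reveal it. The study team also has an expectation: Section 3.4 anticipates inhibition of STAT3 and cyclin D1, in line with the group's own preclinical work in Section 3.3.

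At stake is whether the secondary pharmacodynamic result can be interpreted. Patients undergo two research biopsies for it, each with a goal of at least 3 and up to 8 cores. The efficacy conclusion and patient safety are not at stake.

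**Working it through.** The documents give no sample size, error rate or power for the before/after comparison, so there is no figure to reproduce. The check is by reading, with one illustration of scale.

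**1. What the email lets the recipient do.**
- Subject ID or initials: either one links the two specimens of a pair.
- Collection date or time point: either one puts the pair in order.

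Removing only initials and time point would leave subject ID and date, which still pair and order the specimens. All four items must be replaced.

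**2. Whether anything elsewhere offsets this.**
- Sections 8.4 (randomization and blinding), 11.7 (blinding of study drug) and 15.9 (unblinding) read as not applicable.
- Section 15.8 provides independent review of responses, not of markers.
- Sections 5.3.2 and 14.1.2 refer to the laboratory manual for processing and shipping. Neither refers to it for masking, coding or run layout.
- No section asks for coded specimens, random reading order, a second reader, or both members of a pair in one run.

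**3. Which readouts are exposed.** Section 5.3.2 says the analysis may use some or all of a list. IHC, multiplex IHC and Western blot involve reader judgement. qRT-PCR and RNA-Seq are on the same list and are less exposed.

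**4. Effect on the before/after change.** Let Δ be the true mean change and s the shift in score caused by knowing the time point. The observed mean change estimates Δ + s. With one arm, s cannot be separated from Δ.

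For scale only, suppose Δ = 0 and paired changes are normal, with s toward lower on-treatment scores and equal to d standard deviations of the paired change. The expected share of pairs showing a fall is then Φ(d). The values of d are assumptions; the documents give none.

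| Assumed d | Φ(d) | Expected falls in 10 pairs |
|---|---|---|
| 0 | 0.50 | 5.0 |
| 0.25 | 0.60 | 6.0 |
| 0.50 | 0.69 | 6.9 |
| 0.75 | 0.77 | 7.7 |
| 1.00 | 0.84 | 8.4 |

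This is what a profile plot would show with no drug effect at all.

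**5. Effect on the responder comparison.** The email does not carry response status, so the same s is expected in both groups: (Δ_R + s) − (Δ_N + s) = Δ_R − Δ_N. Adding one constant to every change leaves the ranks, and so the rank sum test, as they were. If changes are cut into categories for Fisher's test, a shift can move some patients across the cut-off. It does so without regard to response, so these comparisons are largely, though not perfectly, protected.

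**The case against.** The strongest reply is that the email is a shipment notice. No section says that the person scoring reads it, and the laboratory manual could specify coding and run layout. That stands as a limit. A reader might infer that scoring will in fact be unmasked, and the documents do not show this. They show that the protocol prescribes disclosure to the laboratory and requires nothing to counter it.

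A reader might also infer an inflated false-positive rate. With 10 pairs, no true change and an assumed shift of 0.3 to 0.5 SD, a nominal 5% paired t-test would reject 13.6% to 29.3% of the time. That is not a property of this trial: Section 17.2 plans no before/after test, and the shift is assumed.

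A third inference is that separate shipments add run-to-run drift in the same direction as treatment. The documents do not support this either. Samples are stored on-site and sent in batches, which can bring a pair together as easily as split it. Accrual runs over about 24 months, so one patient's baseline can be collected after another's Cycle 2 specimen. What remains is that nothing requires the two members of a pair to share a run.

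Finally, phosphorylated STAT3 and cyclin D1 are named only under the exploratory objectives, and the secondary objective names no marker. This lowers the stakes. The biopsies are nevertheless the stated source of the pharmacodynamic analysis.

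**Conclusion.** The point holds as a gap in the protocol and a cheap improvement. The plan sends time point, date and patient identifiers to the laboratory that measures the markers, and requires neither masked scoring nor same-run pairing. The before/after change in judgement-dependent assays, and the plots of it, are therefore open to expectation bias. Reporting the change descriptively does not remove that bias.

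The size is unknown. The illustration above rests entirely on assumed shifts and is not an estimate. The conclusion assumes that at least one of the reader-dependent assays is used and that the laboratory manual adds no masking. If the manual does add it, the remaining task is to state it in the protocol. The primary endpoint is untouched, and the responder versus non-responder comparisons are largely unaffected.

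**What to change.** In Sections 5.3.2 and 14.1.2, identify specimens to the laboratory staff who assay and score them only by a coded specimen number. That number should replace subject ID, initials, collection date and time point together. Hold the key at the coordinating center, outside the laboratory.

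Add this text:

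*For tumor tissue, both specimens of a pair are assayed in the same run in random order and scored without knowledge of patient, time point or clinical response; the key is released after scores are locked.*

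The cost is small. A coding list must be kept, and stored tissue must wait until both members of a pair are available. With a baseline biopsy at the very start of the 28-day screening period, the wait to Cycle 2 Day 8 is at most 28 + 28 + 7 = 63 days, apart from visit windows, treatment delays, or use of an earlier frozen biopsy as Section 5.3.1 allows. Tissue is already fixed or frozen and held on-site for batch shipment, so this fits the existing handling. No extra patients or procedures are needed.
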